3.1. Overall Study Design and Plan

This is an open label safety and tolerability extension study for patients who have completed the TR03 study. Patients will either enter directly into a drug Treatment Period (Worst Itch NRS ≥ 5) or enter an extended screening period of a no-drug Observation Period (Worst Itch NRS < 5) based on their reported NRS scores on the first Visit (Visit 1a). For up to 12 extended screening weeks, patients in the no-drug Observation Period may also transition into the drug Treatment Period if their Worst Itch NRS increases to ≥ 5 .

To allow for various starting levels of pruritus intensity, patients who have a Worst Itch NRS that is ≥ 5 will enter the Treatment Period upon completion of Visit 1a. Patients whose Worst Itch NRS score is < 5 will be entered into an extended screening period, no-treatment criteria Observation Period for up to 12 weeks or until they develop a higher level of pruritus (i.e., Worst Itch NRS ≥ 5), at which point they will transition to the Treatment Period upon completion of Visit 1b. All patients entering the Treatment Period, whether immediately upon study entry or following a period of time in the Observation Period, will initially be titrated to a dose that can be as high as 180 mg twice daily (BID) during the first 4 weeks of the Treatment Period. Patients who continue in the Observation Period and maintain a Worst Itch NRS score of < 5 will be screen failed from the study at the end of the 12-week period. For enrolled patients whose Visit 1a worst itch NRS score satisfies the ≥ 5 enrollment criterion and for whom treatment is initiated, the screening visit Visit 1a will also be designated as the baseline visit. For enrolled patients who must continue into the Observation Period, the first visit during that period when the worst itch NRS ≥ 5 criterion is satisfied will be designated as Visit 1b and that visit will serve as the baseline visit.

The total study duration for any individual patient will be up to 53 weeks. For patients who enter directly into the Treatment Period, the total amount of time on drug will not exceed 50 weeks. Patients who enter the Treatment Period from the Observation Period, the total amount of time spent in the combined two periods of the study cannot exceed 50 weeks. All patients who received drug treatment will have a 2-week Washout and Safety Follow-up period at the end of the dosing period, unless consent is withdrawn.

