The total amount of time in the Observation Period cannot exceed 12 weeks. After these 12 extended screening weeks, patients not eligible for the Treatment Period are screen failed from the study. The study periods are summarized below.

Study Period	Study Weeks	Duration
Observation Period	
Patients who do not meet the criteria to start Treatment are followed in Observation Period visits (OV) for up to 12 extended screening weeks. During this time, the patient may meet criteria and become eligible to enter the Treatment Period. If the patient does not meet the criteria to enter the Treatment Period by the end of 12 extended screening weeks (OV12), participation in the study ends and the patient is screen failed
	Up to 12 Extended Screening weeks
Treatment Period	
For patients directly entering the Treatment Period as of Visit 1a, the Treatment Period begins with Study Week 1 (Visit 1a) and ends with Study Week 50.
 
For patients entering the Treatment Period after being followed in the Observation Period, the number of weeks on treatment and the end of the Treatment Period varies. (See Table 8 in the study protocol for the details of which treatment visits are to take place).
 
The End of Treatment Visit will take place after the patient completes the last week of study drug.
	Up to 50 weeks
Washout and Safety Follow-Up Period	
The Washout and Safety Follow-up Period is two (2) weeks in duration.
 
For patients directly entering the Treatment Period as of Visit 1a and completing 50 weeks of study drug treatment, the Washout and Safety Follow-up Period should take place during weeks 51 and 52.
 
For patients entering the Treatment Period after being followed in the Observation Period, the number of weeks on treatment and the end of the Treatment Period varies; Table 8 in the Study Protocol calculates the Treatment Visit assignments for any patient entering the Treatment Period from the respective Observation Period visits. The Washout and Safety Follow-up Period will take place during the two (2) weeks after the patient completes the last week of study drug.
 
The Washout and Safety Follow-up Period Visit will take place in the week following the completion of the two (2) week Washout and Safety Follow-up Period.
	2 weeks

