3.2.2. Premature Discontinuation of Study Drug Treatment For Reasons Other Than Failure-to-Improve

Patients who complete Study Drug treatment through the End of Treatment Visit 14 (TV14) (even if some doses have been missed or if the patient was followed in the Observation Period before receiving study drug treatment) are considered to have completed Study Drug treatment. Patients discontinuing Study Drug treatment prior to the maximum allowable number of Treatment Weeks (based on their entry into the study at either Visit 1a or Visit 1b) will also be considered to have prematurely discontinued Study Drug treatment. Patients discontinuing Study Drug treatment prior to End of Treatment Visit 14 will be considered to have prematurely discontinued Study Drug treatment and will be asked to complete the End of Treatment Visit (TV14) regardless of where they were in the study visit schedule, the Washout and Safety Follow-up Period Visit and the Premature Discontinuation of Study Drug Telephone Contact visit. Patients removed from the study after enrollment and who have received a dose of study drug will not be replaced.

Some reasons for premature discontinuation of Study Drug treatment include:

- Intercurrent illness
- Any intolerable Adverse Event (AE) that cannot be ameliorated or safely managed with medical intervention or one that poses undue risk to the subject if Study Drug treatment were continued in the opinion of the Medical Monitor or Investigator
- Electrocardiogram (ECG) changes summarized in protocol Section 17.4
- Opioid medication is introduced in anticipation for chronic use of greater than 2 weeks
- Any medication prescribed for chronic anti-pruritic use of greater than 2 weeks
- Development of substance abuse as determined by the Investigator.

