9.1. Adverse Events

Details regarding the definition and reporting of an AE or a serious adverse event (SAE) are provided in the study protocol. AEs will be recorded starting with the signing of the first

informed consent. All AEs will be collected through the Washout and Safety follow up visit (or Early Termination Visit). Following the Washout and Safety follow up visit (or Early Termination Visit), all unresolved AEs that were reported by the Investigator to be probably drug related should be followed by the Investigator until the events are resolved, the patient is lost to follow-up, or the AE has stabilized.

Non-serious AEs that begin during the Observation Period will be captured as medical history in the TR03 extension study; patients who never transition from the Observation Period to the Treatment Period are screening failures and did not complete the early termination or end of study CRFs. SAEs occurring during the Observation Period will be recorded as SAEs.

Also, AEs that were ongoing at the time of a patient's completion of the TR03 core study are recorded as medical history in the TR03 extension study.

A treatment-emergent AE (TEAE) will be defined as one starting or worsening on or after the first dose of study medication during the extension study. If the start date is missing, the event is assumed to be treatment emergent.

For patients who complete study treatment through the Visit 14/End of Treatment visit, Titration Period AEs are those with an onset date from first dose date of the extension study through (first dose date + 27 days). Treatment Period AEs are those with an onset date from first dose date of the extension study through (first dose date + 349 days). Washout and Safety Follow-up AEs are those with an extension study onset date of (first dose date + 350 days) through (first dose date + 363 days). For patients who are treated and who discontinue study drug use prior to the Visit 14/End of Treatment visit yet remain on-study, AEs with an onset date on or after the first dose date of the extension study will be considered Treatment Period AEs.

For the purpose of inclusion in TEAE table summaries, incomplete AE onset and end dates will be imputed as described below.

For incomplete AE onset dates:

- If the day is missing but the month and year are known:
 - If the month and year are different from the month and year of the first dose of study drug, then use the first day of the month as the imputed onset date.

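### SAP 9.1 dates AE periods from first dose and gives early stoppers no washout category, so off-drug AEs are filed as Treatment Period

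*SAP*

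**What the plan says.** Section 9.1 gives three windows for patients who complete treatment through Visit 14:

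- Titration: "Titration Period AEs are those with an onset date from first dose date of the extension study through (first dose date + 27 days").
- Treatment: "Treatment Period AEs are those with an onset date from first dose date of the extension study through (first dose date + 349 days").
- Washout: "Washout and Safety Follow-up AEs are those with an extension study onset date of (first dose date + 350 days"), closing at +363 days.

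For treated patients who stop drug before Visit 14 yet remain on study there is one rule: "AEs with an onset date on or after the first dose date of the extension study will be considered Treatment Period AEs". They have no Washout window and no Titration window.

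The design sections describe the periods differently:

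- Section 3.1 gives every treated patient two weeks of washout after dosing ends, unless consent is withdrawn.
- For patients who come through the Observation Period (at most 12 weeks), "the total amount of time spent in the combined two periods of the study cannot exceed 50 weeks". Section 3.1 says their end of treatment varies and their washout is the two weeks after their last week of drug.
- Section 3.2.2 treats such patients as completers if they reach TV14: those who missed doses "or if the patient was followed in the Observation Period before receiving study drug treatment) are considered to have completed Study Drug treatment".
- Sections 3.2.1 and 3.2.2 send early stoppers to the washout assessment too.
- On the timing of the last visit, section 3.1 says "The Washout and Safety Follow-up Period Visit will take place in the week following the completion of the two (2) week" washout. Section 9.1 collects AEs up to that visit.

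The Treatment/Washout split is used in the AE overview (9.1.1), severity (9.1.3), SAE (9.1.5), special-interest (9.1.6) and abuse-potential (9.1.7) tables. Section 9.1 takes AE percentages over the whole Safety population.

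**The concern.** The fixed offsets describe one kind of patient: direct entry, on drug for exactly 50 weeks. For anyone who finishes sooner, some or all of the off-drug fortnight falls inside the window labelled Treatment. For early stoppers who stay on study, the label does not depend on timing at all.

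Safety is the primary objective, and section 9.1.7 sets out to screen for addiction, abuse potential and withdrawal. Events after cessation are what a Washout column should isolate. Under the stated rule many of them move to Treatment, while the Washout percentage keeps the full Safety population as its denominator. Washout is understated and Treatment is overstated. Off-drug events may also enter the primary description of TEAEs in treatment weeks 5-50 (section 3.3.1), for which section 9.1 defines no separate window.

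**Working it through.** **1. Reproduce the SAP's own windows.** Counting the first dose day as offset 0:

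- Titration, 0 to +27: 28 days = 4 × 7.
- Treatment, 0 to +349: 350 days = 50 × 7.
- Washout, +350 to +363: 14 days, ending at 364 = 52 × 7, which is weeks 51 and 52.

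These are exact for a direct-entry patient treated for 50 weeks.

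**2. Completers with k Observation weeks.** Under the 50-week cap, treatment lasts at most (50 − k) × 7 days. True washout then runs from (50 − k) × 7 to (50 − k) × 7 + 13. The number of washout days at or before +349 is 350 − (50 − k) × 7 = 7k, limited to 14.

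| Observation weeks k | Maximum treatment (days) | True washout offsets | Washout days labelled Treatment |
|---|---|---|---|
| 0 | 350 | +350 to +363 | 0 of 14 |
| 1 | 343 | +343 to +356 | 7 of 14 |
| 2 | 336 | +336 to +349 | 14 of 14 |
| 12 | 266 | +266 to +279 | 14 of 14 |

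Every k from 2 to 12 gives 14 of 14. Treatment shorter than the cap moves washout earlier, so these counts are minimums.

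**3. Early stoppers who remain on study.** A patient who stops at the end of week 13 has the last dose at 13 × 7 − 1 = +90 and washout at +91 to +104. All 14 days are labelled Treatment. The same holds for any stopping time, because the rule has no upper limit.

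**4. The gap at the end.** For a 50-week completer the Washout visit falls in week 53, offsets 52 × 7 = +364 to 53 × 7 − 1 = +370. The Washout window closes at +363. An AE starting from +364 up to that visit is collected but belongs to no period.

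**5. How many patients are affected.** The SAP does not give the inputs, so this is a range under assumptions. Among patients who enter washout, let e be the share who stopped early and o the share of completers who had 2 to 12 Observation weeks. The share whose whole washout is labelled Treatment is s = e + (1 − e) × o.

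| e (assumed) | o = 0 | o = 0.2 | o = 0.5 |
|---|---|---|---|
| 0.2 | 0.20 | 0.36 | 0.60 |
| 0.4 | 0.40 | 0.52 | 0.70 |
| 0.6 | 0.60 | 0.68 | 0.80 |

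For example, 0.2 + 0.8 × 0.2 = 0.36. The share passes one half once o exceeds (0.5 − e)/(1 − e). At e = 0.2 that is 0.3/0.8 = 0.375; at e = 0.4 it is 0.1/0.6 = 0.17.

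If all treated patients enter washout at equal risk, and 1-week entrants and visit-week onsets are ignored, the table shows about (1 − s) of the true Washout incidence. Over this grid that is from 0.80 down to 0.20 of it.

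**The case against.** The best defence is that only period labels move. Overall TEAE, SAE and abuse-potential counts stay the same, including onsets in the week-53 gap. All AEs are listed, and section 9.1.7 reports days from start of treatment to onset. The dedicated withdrawal instrument, the SOWS, is tied to the End of Treatment visit and, for discontinued patients, to the two weeks after last dose (section 9.2.1), so it is untouched. The study is single-arm and descriptive, with no inference. All of this stands and limits the harm, but it does not make the by-period tables right.

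Several limits on scope also stand. The early-stopper rule covers only those who remain on study; a patient who withdraws consent or leaves at early termination has no washout AEs to misfile. Section 3.1 gives a cap on treatment rather than exact lengths, and leaves visit assignment to the protocol's Table 8, so the day counts above rest on that cap.

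A reader might infer that most washout AEs are misfiled. The SAP does not support that: it states neither the early-stop rate nor the Observation share, and the grid falls on both sides of one half. A reader might also infer that only direct-entry 50-week completers can ever supply a Washout AE. That fails too. A completer with 1 Observation week treated to the cap keeps +350 to +356 as Washout, and one with 2 Observation weeks has a visit week at +350 to +356, which is also labelled Washout.

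Finally, counting events for a short lag after the last dose of an extended-release product as on-treatment is a recognised convention. But such a lag would be tied to last dose, which the present rule is not.

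**Conclusion.** The rule in section 9.1 is wrong as written, because it contradicts the SAP's own account of when washout occurs. Three groups are certainly affected:

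- early stoppers who remain on study: all washout AEs;
- completers with 2 to 12 Observation weeks: all 14 washout days;
- completers with 1 Observation week: at least 7 of 14 days.

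The last two take treatment as at most 50 minus the Observation weeks. In addition, 50-week completers have up to a week before the Washout visit that is assigned to no period.

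The direction of the error is clear: Washout events are understated against a whole-Safety-population denominator, and off-drug events are added to Treatment, possibly also to the weeks 5-50 description. Its size cannot be stated from the SAP. The error is confined to the by-period presentation.

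**What to change.** Amend section 9.1 so that one set of definitions covers every treated patient, completer or not:

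- **Treatment Period AE:** onset from first dose through the patient's actual last dose date, derived as in section 7.3.2.
- **Washout AE:** onset from the day after last dose through the Washout and Safety Follow-up visit, or last contact if that visit does not take place.
- **Titration AE:** onset from first dose to +27 days, or to last dose if earlier.
- **Washout denominator:** patients who entered washout, stated as an exception to the Safety-population rule.

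Direct-entry patients treated for exactly 50 weeks keep +350 to +363 as Washout, extended to their visit, which closes the gap.

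The cost is a revised derivation and a new denominator across the overview, severity, SAE, special-interest and abuse-potential tables. No new data are needed: the last dose date is already on the eCRF with a fallback rule, and section 8.6 already uses it to date discontinuation during treatment.

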3.3. Study Endpoints

3.3.1. Primary Endpoint

The primary endpoint is a description of the overall incidence and nature of treatment-emergent adverse events (TEAEs) during treatment weeks 5-50.

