 - If the month and year are the same as the month and year of the first dose of study drug, and the end date (after any imputation) is on or after the first dose of study drug, then use the date of the first dose of study drug as the imputed onset date.
 - If the month and year are the same as the month and year of the first dose of study drug, and the end date (after any imputation) is prior to the date of the first dose of study drug, then use the end date as the imputed onset date.
- If the month is missing but the year is known (day can be either missing or known):
 - If the year is different from the year of the first dose of study drug then use Jan. 1st of the reported year as the imputed onset date.

- If the year is the same as the year of the first dose of study drug and the end date (after any imputation) is on or after the first dose of study drug then use the date of the first dose of study drug as the imputed onset date.
- If the year is the same as the year of the first dose of study drug and the end date (after any imputation) is prior to the date of the first dose of study drug, then use the end date as the imputed onset date.
- If the start date is completely missing, the event is assumed to be treatment-emergent.

For incomplete AE end dates:

- If the day is missing but the month and year are known then use the last day of the month as the imputed end date.
- If the month is missing but the year is known (and the day is either missing or known) then use Dec. 31st of the year as the imputed end date.

Adverse events will be coded according to MedDRA (version to be delineated in the clinical study report).

All AE summary tables will present system organ class (SOC) and preferred term (PT), will include counts of patients, and will be based on TEAEs. SOC will be displayed in descending order of frequency overall and then alphabetically. PT will be displayed in descending order of frequency overall and then alphabetically within SOC. A patient with two or more AEs within the same level of summarization will be counted only once in that level using the most extreme incident. Percentages will be based on the number of patients in the safety population.

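### The partial-onset rules in SAP 9.1 suit the treatment-emergent flag but also allocate AEs to study periods, which can distort a weeks 5-50 count; a wholly missing start date is flagged with no end-date check

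*SAP*

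**What the plan says.** The primary endpoint (SAP 3.3.1) is the "overall incidence and nature of treatment-emergent adverse events (TEAEs) during treatment weeks 5-50".

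Section 9.1 allocates the AEs of patients who complete treatment by onset date. Titration runs from first dose to first dose + 27 days, the Treatment Period from first dose to + 349 days, and Washout and Safety Follow-up from + 350 to + 363 days. Section 9.1.1 states that titration lies inside the Treatment Period and that its events are reported in both. No reporting period for weeks 5-50 alone is defined.

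Partial dates are covered by one statement: "For the purpose of inclusion in TEAE table summaries, incomplete AE onset and end dates will be imputed as described below". The onset rules in 9.1 are:
- Day missing, month differs from the first-dose month: 1st of the reported month.
- Month missing (whether or not the day is known), year differs from the first-dose year: 1 January.
- Same month (or same year, if the month is missing) as first dose, event ended on or after first dose: "use the date of the first dose of study drug as the imputed onset date".
- Same month or year, event ended before first dose: the end date.
- No start date at all: "If the start date is completely missing, the event is assumed to be treatment-emergent". The definition of a TEAE earlier in 9.1 says the same. Neither statement looks at the end date.

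**The concern.** An early imputed date is the cautious choice when the question is whether an event began on treatment. It is not cautious when the question is which treatment period the event belongs to. The period summaries in 9.1.1 and 9.1.3 are TEAE tables, so the imputation statement reaches them, and the SAP gives no other rule for placing a partial date. A summary confined to weeks 5-50 would therefore use dates designed for another purpose. Events could be lost from the primary window and titration incidence raised.

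Two further consequences follow from the same text. Sections 9.1.6 and 9.1.7 tabulate days to first onset and duration, again with no other date rule. If imputed dates feed those tables, an unknown onset can appear as Day 1. And an event with no start date but a recorded end before first dose is called treatment-emergent, although the partial-date rules would place it before first dose.

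**Working it through.** **Inputs (SAP 3.3.1 and 9.1).** Week 4 ends at offset 4 × 7 - 1 = 27, week 50 at 50 × 7 - 1 = 349 and week 52 at 52 × 7 - 1 = 363. These match the SAP's offsets. Titration is Days 1-28, weeks 5-50 are Days 29-350 (350 - 28 = 322 days) and washout is Days 351-364 (14 days). The SAP states no figure for the effect of imputation, so there is none to reproduce.

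**Method.** The onset rules were applied to every true onset day from 1 to 364, for each of the 365 first-dose dates in 2015. Assumptions: a completer on the full 50-week schedule, uniform onset over the days, and an end date on or after first dose. The table gives average days per first-dose date.

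| True period → imputed period | Day missing | Month missing |
|---|---|---|
| Titration → titration | 28.0 | 28.0 |
| Weeks 5-50 → titration | 14.72 | 179.53 |
| Weeks 5-50 → weeks 5-50 | 307.28 | 142.47 |
| Washout → titration | 0 | 1.36 |
| Washout → weeks 5-50 | 10.55 | 12.35 |
| Washout → washout | 3.45 | 0.29 |

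**Outflow at Day 28/29.** Day missing: 14.72 / 322 = 4.6%. Month missing: 179.53 / 322 = 55.8%. No titration onset moves into weeks 5-50.

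**Net of the inflow at Day 350/351.**
- Day missing: 10.55 - 14.72 = -4.17 days, and -4.17 / 322 = -1.3%. By start date the net runs from -18 to +14 days: positive for 168 dates, zero for 12, negative for 185. The two flows balance if the daily AE rate in washout is 14.72 / 10.55 = 1.4 times that in the window.
- Month missing: 12.35 - 179.53 = -167.18 days, and -167.18 / 322 = -51.9%. The range is -322 to +14 days: positive for 14 dates, zero for 1, negative for 350. Balance would need a washout rate 179.53 / 12.35 = 14.5 times that in the window.

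**Examples.**
- First dose 10 Jan 2015, true onset 20 Feb 2015 (Day 42). With the day missing the onset becomes 1 Feb, Day 23: out of the window.
- First dose 1 Jul 2015, true onset 20 Jun 2016 (Day 356, washout). With the day missing it becomes 1 Jun 2016, Day 337; with the month missing, 1 Jan 2016, Day 185. Both are inside weeks 5-50.
- First dose 15 Jan 2016, onset recorded only as 2016, event ended after first dose. The imputed onset is Day 1. Day 29 is 12 Feb, Day 350 is 29 Dec and 31 Dec is Day 352, so 322 of the 352 possible on-study days (91.5%) lie in weeks 5-50. If the end date is also only 2016, it becomes 31 Dec and the apparent duration is 352 days.

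**Missing start date.** With a partial start in the first-dose month or year and an end before first dose, the end date becomes the onset and the event is not treatment-emergent. With no start date and the same end date, it is treatment-emergent. Section 7.1 does look at the end date when a medication's start is missing.

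**The case against.** A reader might infer that imputation always picks the earliest day, can only remove events from weeks 5-50, and so understates the primary endpoint. The documents do not support that.
- When an event ended before first dose, the end date is used, which is the latest possible onset. A wholly missing onset receives no date.
- Washout onsets are pulled into weeks 5-50. With only the day missing this nearly offsets the outflow.
- The Treatment Period table includes titration, so an event moved to Day 1 stays in it and that table is not lowered. For treated patients who stop drug early but remain on study, all AEs from first dose are Treatment Period AEs.
- Section 9.1 counts a patient once per level, so a shifted event changes incidence only if the patient has no other event in the window at that level.
- The SAP gives no frequency of partial dates. The 4.6% and 55.8% apply only to events whose onset date is incomplete in that way.

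All of this stands, and it limits the claim to what can happen. It does not remove the point. Pulling washout events in is itself misallocation, and it needs onsets after Day 350. Patients whose follow-up ends by then have no such inflow, so at the window's boundaries their shift is outward only.

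Two other objections hold in part. The missing-start defect is narrow: 9.1 records non-serious Observation Period AEs and AEs ongoing from TR03 as medical history, which leaves mainly Observation Period SAEs, and it raises TEAE counts rather than lowering them. The effect on 9.1.6 and 9.1.7 is conditional on imputed dates being used there, which the SAP neither states nor excludes.

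**Conclusion.** The point holds in limited form and is minor. Rules built to decide treatment-emergence also allocate events to periods. At Day 28/29 they work in one direction, out of weeks 5-50; at Day 350/351 they work inward. With the day missing the net is about -1.3% of the window and its sign depends on the start date. With the month missing it is about -167 of 322 days and negative for 350 of 365 start dates. A weeks 5-50 count can therefore be understated and titration incidence inflated, mainly through month-missing dates; it cannot be said that the endpoint is understated. The figures rest on a full-schedule completer, uniform onset and an end date on or after first dose. The effect on the reported incidence cannot be sized without the number of partial dates. The missing-start rule is inconsistent with the partial-date rules whatever the numbers.

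**What to change.** In Section 9.1:
1. State that imputed onset dates serve the treatment-emergent flag only.
2. Add to both statements of the missing-start rule an exception for events whose known end date is before first dose.
3. Define the weeks 5-50 primary summary. Report separately the events whose recorded partial date fits more than one period, and give a sensitivity count that includes them in weeks 5-50. That count should not be the main figure, because it would also take in true titration and washout events and bias the result upward.

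In Sections 9.1.6 and 9.1.7, state that imputed dates are not used for days to onset or duration.

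The cost is a few sentences, minor programming, and a footnoted range in place of a single weeks 5-50 figure.
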